10.1.2 Study Termination and Closure

This study may be prematurely terminated if there is sufficient reasonable cause, including but not limited to:

- Determination of unexpected, significant, or unacceptable risk to participants
- Insufficient compliance to protocol requirements
- Data that are not sufficiently complete and/or evaluable
- Regulatory authorities

If the study is prematurely terminated, the Principal Investigator (PI) will promptly inform study participants and the Institutional Review Board (IRB) and regulatory authorities as applicable. Study participants will be contacted, as applicable, and be informed of changes to study visit schedule. The PI will assure appropriate follow-up for the subjects, as necessary.

The sponsor will notify regulatory authorities as applicable.

10.1.3 Confidentiality and Privacy

Subject confidentiality is strictly held in trust by the site PIs, other study personnel, the sponsor, and their agents. This confidentiality includes documentation, investigation data, subject's clinical information, and all other information generated during participation in this trial. No information concerning this trial, or the data generated from this trial, will be released to any unauthorized third party without prior written approval of the subject and NTI.

Subject confidentiality will be maintained when trial results are published or discussed in conferences and is extended to cover testing of samples/specimens. The study monitor or other authorized representatives of NTI as well as governmental regulatory agencies, such as the FDA, may inspect all documents and records required to be maintained by the site PI. This includes, but is not limited to, medical records (office, clinic or hospital) and pharmacy records for the subjects in this trial. The participating site will permit access to such records.

All records will be kept locked and all computer entry and networking programs will be carried out with coded numbers only and with password-protected systems. All non-clinical samples/specimens, evaluation forms, reports, and other records that leave the site will be identified only by a coded number and will not be identified by the subject's name.

As this research is funded by the NIH, it is covered by NIH policy which effectively issues the research a Certificate of Confidentiality. By this policy, researchers cannot be forced to disclose or provide, in any Federal, State, or local civil, criminal, administrative, legislative, or other proceeding, the name of such individual or any such information, document, or biospecimen that contains identifiable, sensitive information about the individual and that was created or compiled for purposes of the research, unless such disclosure or use is made with the consent of the individual to whom the information, document, or biospecimen pertains.

The Certificate cannot be used to resist a demand for information from personnel of the United States Government that is used for auditing or evaluation of federally funded projects, like this study, or for information that must be released in order to meet the requirements of the Federal Food and Drug Administration (FDA).

A Certificate of Confidentiality does not prevent the subject from voluntarily releasing information about themselves or their involvement in this research. If any person or agency obtains a written consent to receive research information, then the researchers may not use the Certificate to withhold that information.

The Certificate of Confidentiality does not prevent the researchers from reporting without the subject's consent, information that would identify the subject as a participant in the research project regarding matters that must be legally reported including: child and elder abuse, sexual abuse, or wanting to harm themselves or others.

The release of individual private information or specimens for other research will only occur if consent was obtained from the individual to whom the information, document, or biospecimen pertains, *or* for the purposes of other

research that the release is in compliance with applicable Federal regulations governing the protection of human subjects in research.

10.1.4 Future Use of Stored Specimens for Secondary Research

Subjects will be asked to consent to use of any remaining specimens for possible use in future secondary research studies as a condition of their study participation. A subject’s decision can be changed at any time prior to the end of the study by notifying the study doctors or nurses in writing. However, if a subject consents to future use and some of their blood has already been used for research purposes, the information from that research may still be used.

Some samples may be stored at the local site and some at a central clinical storage facility. Samples may be shared with other investigators at other institutions. The samples will not be sold or used directly for production of any commercial product. No genetic testing will be performed on stored specimens.

Each sample will be encoded (labeled) only with a barcode and a unique tracking number to protect subject’s confidentiality. There are no benefits to subjects in the collection, storage and subsequent research use of specimens. Reports about future research done with subject’s samples will not be kept in their health records.

10.1.6 Safety Oversight

10.1.6.1 Safety Monitoring Committee (SMC)

The study oversight will be conducted by a SMC which is an independent group of experts that will be established by NTI to monitor subject safety and advise NTI. SMC members will be separate and independent of study personnel participating in this study and should not have scientific, financial or other conflicts of interest related to the study. The SMC will consist of members with appropriate expertise to contribute to the interpretation of the data from this trial.

The primary responsibilities of the SMC are to:

- Review and evaluate the accumulated study safety data in a blinded fashion for participant safety after the low dose cohort prior to proceeding to the high dose cohort, study conduct and progress, and
- Make recommendations to the sponsors concerning the continuation, modification, or termination of the trial.

The operating rules of the SMC will be established in conjunction with NTI guidelines.

The SMC will review the safety laboratory results, reactogenicity data, and adverse event information collected through day 15 following Dose 2 for the Low Dose Cohort. SMC approval is required prior to initiation of enrollment in the High Dose Cohort.

The SMC may also be asked to review safety information on the low dose or high dose sentinel groups as documented in Section [10.1.6.2](#).

NTI or the SMC may convene the SMC on an ad hoc basis according to protocol criteria or if there are immediate concerns regarding observations during the course of the study. Any AE/SAE that triggers a study halting rule will be reviewed by the Emmes BMM within 24 hours of its being reported, and, after confirming that a study halting rule was met, Emmes will alert the SMC chair to the situation and will provide a written narrative of the safety event. In addition, Emmes will notify the site PI that a halting rule has been triggered, and, upon approval by the SMC chair, will instruct the study site to suspend both study enrollment and study interventions (i.e., administering vaccine to subjects) until NTI provides explicit directions for resuming the suspended study activities. Concurrent with notification to the study site, Emmes will inform NTI that a halting rule has been triggered and that study activities, excepting follow-up with subjects for safety monitoring, have been paused pending the SMC's review of the inciting event. The SMC will conduct an expeditious review of all relevant information, and a written summary of the committee's discussion, to include any abiding concerns for subject safety, as well as any recommendations by the SMC regarding study continuation, will be submitted by Emmes to NTI. Any decision to suspend study enrollment and/or study interventions, either temporarily or permanently, is exclusively NTI's.

The SMC will review SAEs on a regular basis and ad hoc during the study.

10.1.6.2 Internal Safety Review Committee (ISRC)

An internal safety review committee (ISRC), consisting of the blinded medical monitor, clinical program manager and the PI may be convened to provide an option for a rapid review of safety data collected through the day 8 visit following dose one administered to the sentinel cohort of the low dose group and the sentinel cohort of the high dose group. If within the sentinel group during the period from first vaccination through the day 8 visit, no individual halting rule was met, and no more than one unique Grade 3 adverse event (i.e., no same adverse event in more than one subject) was observed then the study will continue with administration of the second vaccination to the sentinel group and initiation of enrollment in the expanded dose cohort. The ISRC may be convened to assist with this objective determination. If the criteria above will not be met, or at the request of the PI and/or NTI, the SMC will be convened to review the sentinel safety data. If the SMC is convened for any reason for review of the sentinel data, the ISRC will not be convened for the cohort and the SMC will determine whether administration of the second vaccination to the sentinel cohort and initiation of enrollment in the expanded dose cohort in order for additional study vaccinations is to be given.

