7.1 Halting Criteria and Discontinuation of Study Intervention

7.1.1 Study Halting Criteria

Additional enrollment and study interventions/administration of study products in this trial will be halted for SMC review/recommendation if any of the following are reported:

- Any subject experiences ulceration, abscess, or necrosis at the injection site related to study product administration.
- Any subject presents with laryngospasm, bronchospasm, hypotension or anaphylaxis occurring within 24 hours following product administration that is considered related to study product.
- Two or more subjects experience generalized urticaria (defined as occurring at more than two body parts) within 72 hours after administration of study product that is considered related to study product.
- Any subject experiences an SAE after administration of study product and prior to the subject's last visit that is considered related to study product.
- Two or more subjects who received at least one dose of study vaccine to date, cumulative to all study vaccine administrations, across all treatment arms, experience the same Grade 3 (unsolicited AE or safety laboratory), in the same HLT by MedDRA coding, considered related to study product.

This trial will also be halted for SMC review/recommendation if, within 7 days after administration of either study vaccination, any of the following occurs:

- Three or more subjects who received at least one dose of study vaccine to date, cumulative to all study vaccine administrations, across all treatment arms, experience the same severe (Grade 3) study vaccine-related injection site reaction. Erythema and induration (hardness)/edema (swelling) will also be measured in mm but size will not be used as halting criteria.
- Three or more subjects who received at least one dose of study vaccine to date, cumulative to all study vaccine administrations, across all treatment arms, experience the same severe (Grade 3) study vaccine-related subjective systemic reaction, for which the severity (grade) is corroborated by study personnel.
- Three or more subjects who received at least one dose of study vaccine to date, cumulative to all study vaccine administrations, across all treatment arms, experience the same severe (Grade 3) study vaccine-related quantitative systemic reaction.

Grading scales for solicited injection site and systemic (subjective and quantitative) reactions are included in Section [8.5.1.1](#).

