7.1.2 Individual Halting Criteria

Individual Halting Criteria must be reviewed by the site PI prior to administration of the second study vaccination for each subject. It is the responsibility of the site to ensure that any subject meeting the below criteria are discontinued from receiving study product; however, the Emmes BMM or safety monitor may be consulted as needed.

The second study vaccination will not be administered to a subject if any of the following criteria are met, as determined by the site PI:

- Serious adverse event associated with study vaccination.
- Pregnancy in a female subject.
- Type 1 hypersensitivity associated with study product.
- Grade 3 systemic reaction associated with study product.
- Grade 3 local reaction (with the exception of erythema/induration) associated with study product (e.g., pain).
- Grade 2 or higher fever within the first 24 hours following the initial vaccination.
- Medical condition for which continued participation, in the opinion of the site principal investigator or appropriate sub-investigator, would pose a risk to the subject or would be likely to confound interpretation of the results.
- Presence of signs or symptoms that could confound or confuse assessment of study vaccine reactogenicity. For subjects with injection site or systemic signs or symptoms, or with an acute illness, including but not limited to an oral temperature greater than or equal to 100.4°F, the second study vaccination should be postponed/deferred until signs, symptoms, or acute illness have resolved and still within the acceptable protocol-specified window for that visit. If outside this window, the Blinded Medical Monitor must first approve the second study vaccination and the documentation of approval should be filed in the subject's chart.
- Any unresolved or continuing solicited or unsolicited Grade 3 adverse event after first vaccination. An unresolved or continuing Grade 1 or Grade 2 adverse event is permissible unless, in the opinion of the site principal investigator or appropriate subinvestigator, it would render study vaccination unsafe or interfere with the evaluation of responses.
- Grade 2 or higher clinical safety laboratory result that does not decrease to Grade 1 or below prior to the second study vaccination. For a subject to receive the second study vaccination, the most recently evaluated clinical safety laboratory values obtained prior to the second study vaccination must be Grade 1 or less. The

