second study vaccination should be scheduled to occur within the acceptable protocol-specified window for that visit. If outside this window, the Blinded Medical Monitor must first approve the second study vaccination and the documentation of approval should be filed in the subject's chart.

- Grade 3 adverse event that occurs without alternative etiology in the 7 days following the first study vaccination.
- Severe or sustained reaction or disability related to the first study vaccination.
- New information becomes available that makes further participation unsafe.

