8.5.3.2 Relationship to Study Intervention

The licensed study physician's assessment of an AE's relationship to study product is part of the documentation process, but it is not a factor in determining what is or is not reported in this study. If there is any doubt as to whether a clinical observation is an AE, the event should be reported. The relationship to study product must be assessed for AEs using the terms: related or not related. In general, the study product must always be suspect. To help assess, the following guidelines are used:

- Related – The AE is known to occur with the study intervention, there is a reasonable possibility that the study intervention caused the AE, or there is a temporal relationship between the study intervention and event. Reasonable possibility means that there is evidence to suggest a causal relationship between the study intervention and the AE.
- Not Related – There is not a reasonable possibility that the administration of the study intervention caused the event, there is no temporal relationship between the study intervention and event onset, or an alternate etiology has been established.

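### The sentinel go/no-go rule gives its Grade 3 limit in two forms that are not equivalent: a cap of one event, and a bar only on the same event in more than one subject

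*Protocol*

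**What the plan says.** Protocol Section 10.1.6.2 sets the gate between the first vaccination of a sentinel group (three vaccine, one placebo) and the next step, which is dose 2 for those four subjects and enrollment of the expanded cohort. Two conditions must hold from first vaccination through the Day 8 visit. No individual halting rule may have been met, and the group must have shown "no more than one unique Grade 3 adverse event (i.e., no same adverse event in more than one subject". The Grade 3 condition is not limited to events judged related to the product.

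The section treats the decision as mechanical: "The ISRC may be convened to assist with this objective determination". It also gives the consequence of failing: "If the criteria above will not be met, or at the request of the PI and/or NTI, the SMC will be convened".

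The other descriptions of the sentinel review are protocol Sections 1.1.3, 1.1.8 (with Table 1, footnote 3), 4.1 and 9.4.4.1, and SAP Section 4.1. None states a Grade 3 limit. Several point back to Section 10.1.6 or to the protocol as a whole. The word *unique* is not defined in either document.

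**The concern.** The abbreviation *i.e.* presents the two halves of the Grade 3 condition as the same thing, and they are not. Suppose one sentinel has a Grade 3 headache and another has Grade 3 nausea, and neither event meets an individual halting rule. That is two Grade 3 events, so a cap of one is exceeded and the SMC must be convened. No event has occurred in more than one subject, so the parenthetical rule is satisfied and the study proceeds.

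This is a first-in-human trial, and the gate controls both a second exposure for the sentinels and the first exposure of the remaining subjects at that dose. A rule described as objective should give one answer on one set of data. Here two careful readers could disagree on whether independent review is mandatory.

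**Working it through.** The plan gives no operating characteristic for this rule, so there is no figure to reproduce. The check has three steps.

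**1. Do the two halves give the same decision?** Take only Grade 3 events that meet no individual halting rule, because any other event already fails the first condition.

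- Cap: continue if the sentinel group has at most one Grade 3 event.
- Gloss: continue if no Grade 3 event type occurs in more than one subject.

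| Grade 3 events among the four sentinels | Cap | Gloss |
|---|---|---|
| None | continue | continue |
| One | continue | continue |
| Two different events, in two subjects | SMC | continue |
| Two different events, in one subject | SMC | continue |
| Same event in two subjects | SMC | SMC |
| Same event twice in one subject | SMC | continue |
| Four different events, one per subject | SMC | continue |

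The halves agree up to one event. With exactly two events there are four patterns, and the halves differ in three of them. One of those three, a repeat of the same Grade 3 event in one subject within about a week, is marginal. The clearest conflict is two different events in two subjects.

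**2. Does another section settle it?** The sections listed above set no Grade 3 limit. Section 7.1.1 has four Grade 3 study-halting rules, and all count the same event across subjects. One, for example, applies when two or more subjects "experience the same Grade 3 (unsolicited AE or safety laboratory), in the same HLT by MedDRA coding, considered related to study product". These are study-wide rules confined to related events. They suggest what the drafter may have had in mind, but they do not say how to read the sentinel gate.

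**3. Which events does the conflict reach?** Section 7.1.2 already covers product-associated Grade 3 systemic reactions and most product-associated Grade 3 local reactions. It also covers:

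- "Grade 3 adverse event that occurs without alternative etiology in the 7 days following the first study vaccination";
- "Any unresolved or continuing solicited or unsolicited Grade 3 adverse event after first vaccination".

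Day 8 is 8 − 1 = 7 days after Day 1, so the seven-day rule spans essentially the whole sentinel window, apart from the one-day visit allowance. Section 8.5.3.2 makes relatedness the default: "In general, the study product must always be suspect", and a temporal relationship is enough. In the week after vaccination a temporal relationship will nearly always be present. The main way out is the last limb of the not-related definition, "or an alternate etiology has been established".

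What remains is mainly Grade 3 events that have resolved and that the investigator attributes to another cause. The Grade 3 clause of Section 10.1.6.2 has an effect of its own mainly on these events, and with two or more of them its halves can disagree.

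**The case against.** The strongest defence is that a single coherent reading exists. *I.e.* introduces a definition, so the clause means that any given Grade 3 event may appear in at most one subject. On that reading *unique* does some work, whereas on a plain cap it is redundant. Same-event counting in Section 7.1.1 points the same way. This stands as far as intent goes: the gloss may well be the rule the sponsor wanted. It does not remove the problem, because the main clause still reads naturally as a total of one and nothing tells the reader to set that aside.

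It is also fair to say that the individual halting rules do nearly all the work and that human review sits on top. Section 4.1 says the internal committee's review will take place and requires approval. The principal investigator or sponsor can call in the SMC under Section 10.1.6.2, and it can meet ad hoc under Section 10.1.6.1. A reader might infer that subjects could receive dose 2 with nobody having looked at the events. The documents do not support that. These safeguards rest on judgment, however, and none says which limit makes SMC review compulsory.

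Two further inferences go too far. One is that the conflict also runs in reverse: if *unique* means a distinct type, the same event in two subjects would pass the main clause. The parenthesis in the same clause expressly forbids that outcome, so no one reading the whole sentence could apply it. The other is that disagreement in three of four two-event patterns shows the conflict is common. The patterns are not equally likely, and the count describes the wording only.

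Finally, SAP Section 2 describes the increase to 5 mcg in the past tense. At least the Group 1 sentinel decision may therefore already have been made, which limits the practical benefit of a change.

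**Conclusion.** The concern holds as a minor defect in a stated decision rule. The two forms of the Grade 3 limit give opposite decisions when the sentinels have two different Grade 3 events that meet no individual halting rule, and neither document says which form governs.

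The reach is narrow, mainly resolved Grade 3 events attributed to an alternative cause in a group of four healthy adults over about a week. The frequency is probably low but cannot be quantified. The documents give no Grade 3 rate, and any figure built on an assumed rate would also have to allow for the events that Section 7.1.2 removes first. The conclusion rests on the wording alone and assumes no event rate. It does not show that the sponsor intended the stricter limit, or that any sentinel decision was wrong.

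**What to change.** Replace the clause in Section 10.1.6.2 with a single criterion. The conservative version is:

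*Convene the SMC if any individual halting rule is met, or if two or more Grade 3 adverse events, of the same or different type, occur among the sentinel subjects through the Day 8 visit.*

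This satisfies both halves, since the same event in two subjects is also two events, so the SMC is convened whenever either half would require it. State as well whether several Grade 3 symptoms of one illness in one subject count as one event.

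If the sponsor intended only the same-event rule, delete the leading words that set a maximum of one and state that rule alone. Either choice removes the ambiguity. For any sentinel review already completed, record which reading was applied.

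The cost is one sentence of protocol wording and, under the conservative version, an occasional extra SMC review.
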